14.3.7.2.2 PCI Values

Electrocardiogram values will be considered PCI if they meet or exceed the criteria listed in Table 6. The number and percentage of subjects with PCI values will be summarized at each scheduled post-Baseline visits and for overall post-Baseline.

For the by-visit summary, the numerator for the percentage is the number of subjects with a post-Baseline PCI value for the given parameter, visit and treatment group, and the denominator is the number of subjects with non-missing values for the given parameter, visit and treatment group.

For the overall post-Baseline summary, the numerator for the percentage is the number of subjects with at least 1 post-Baseline PCI value for the given parameter and treatment group, and the denominator is the number of subjects with at least 1 post-Baseline value for the given parameter and treatment group; all post-Baseline values will be considered, including unscheduled and out-of-window values.

A listing of all PCI values will be provided for those subjects and parameters for which at least 1 PCI value (including Baseline) was observed.

Table 6 Criteria for Potentially Clinically Important ECG Values

ECG Parameter	Unit	High PCI Criteria
QRS Interval	msec	≥120
PR Interval	msec	≥220
QTcB or QTcF	msec	>500
QTcB or QTcF: change from baseline	msec	>60

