4.3 Exclusion Criteria

A subject must not meet any of the following exclusion criteria to be eligible for the study:

- 1. Is in hospice, is receiving end-of-life palliative care, or is bedridden
- 2. Has neuropsychiatric symptoms that are primarily attributable to current delirium or substance abuse (i.e., neuropsychiatric symptoms not related to neurodegenerative disease)
- 3. Has current evidence of an unstable neurological, cardiovascular, respiratory, gastrointestinal, renal, hepatic, hematologic, or other medical disorder, including cancer or malignancies that, in the judgment of the Investigator, would jeopardize the safe participation of the subject in the study or significantly interfere with the conduct or interpretation of the study
- 4. Has a history of epilepsy

Final Version: 1.0 Date: 5 March 2021

- 5. Has atrial fibrillation unless adequately anticoagulated
- 6. Has a history of myocardial infarction, unstable angina, acute coronary syndrome, or cerebrovascular accident within the last 6 months prior to Visit 1 (Screening)
- 7. Has any of the following:
 - a. greater than New York Heart Association (NYHA) Class 2 congestive heart failure (Appendix J)
 - b. Grade 2 or greater angina pectoris (by Canadian Cardiovascular Society Angina Grading Scale) (Appendix K)
 - c. sustained ventricular tachycardia
 - d. ventricular fibrillation
 - e. torsades de pointes
 - f. syncope due to an arrhythmia
 - g. an implantable cardiac defibrillator
- 8. Has a history of human immunodeficiency virus (HIV) or hepatitis C infection
- 9. Has a history of neuroleptic malignant syndrome or serotonin syndrome
- 10. Has a known personal or family history of long QT syndrome or family history of sudden cardiac death
- 11. Has any of the following ECG results at Visit 1 (Screening) or Visit 2 (Baseline):
 - a. If the subject is **not** on citalogram, escitalogram, or venlafaxine:
 - i. QTcF >450 ms, if QRS duration <120 ms
 - ii. QTcF >470 ms, if QRS duration ≥120 ms
 - b. If the subject is on citalogram, escitalogram, or venlafaxine:
 - i. QTcF >425 ms, if QRS duration <120 ms
 - ii. QTcF >450 ms, if QRS duration \geq 120 ms

At Screening, if the set of triplicate ECGs has a prolonged QTcF due to an identifiable cause, and it is medically appropriate to address that cause, a repeat set of triplicate ECGs may be performed during Screening at the discretion of the Medical Monitor.

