14.3.5.2 Shift Tables

Laboratory values will be summarized in shift tables to determine the number and percentage of subjects with values classified as below (low), within (normal), or above (high) normal ranges at each scheduled post-Baseline visit relative to the same classification at the Baseline visit. For the by-visit shift summary, the denominator is the number of subjects with non-missing values at Baseline and the given visit for the given parameter and treatment group.

The shifts from Baseline to overall post-Baseline minimum and maximum will also be presented. The denominator is the number of subjects with non-missing Baseline and at least 1 post-Baseline value for the given parameter and treatment group.

For hemoglobin, hematocrit and uric acid, by-visit as well as overall post-Baseline minimum and maximum will be presented for each gender as well as for both genders combined.

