14.3.5.3 Potentially Clinically Important (PCI) Laboratory Values

The number and percentage of subjects with PCI laboratory values at scheduled post-Baseline visits Week 4 and Week 8 and overall post-Baseline will be summarized by Baseline status (all or within normal range) for selected parameters. PCI criteria are listed in Table 3 and Table 4. Subjects with multiple PCI values for a given parameter will be counted only once for that parameter. All post-Baseline values will be considered, including unscheduled and out of window values

For the by-visit summary, the numerator for the percentage is the number of subjects with a post-Baseline PCI value for the given parameter, visit, and treatment group, and the denominator is the number of subjects with non-missing values for the given parameter, visit, and treatment group. For the overall post-Baseline summary, the numerator for the percentage is the number of subjects with at least 1 post-Baseline PCI value for the given parameter and treatment group, and the denominator is the number of subjects with at least 1 post-Baseline value for the given parameter and treatment group. For hemoglobin, hematocrit and uric acid, the count and percentage of subjects with PCI values will be presented for each gender as well as for both genders combined.

Table 3 Criteria for Potentially Clinically Important Laboratory Values – Hematology and Chemistry

Analyte	Conventional Unit	Low PCI Criteria	High PCI Criteria	SI Unit	Low PCI Criteria	High PCI Criteria	
	Hematology (whole blood)						
Hemoglobin (male)	g/dL	<11	>18	g/L	<110	>180	
Hemoglobin (female)	g/dL	<10	>17	g/L	<100	>170	
Hematocrit (male)	%	<30	>55	L/L	< 0.3	>0.55	
Hematocrit (female)	%	<30	>50	L/L	< 0.3	>0.5	
Leukocyte (White Blood Cell Count)	x 10 ³ /uL	≤2.8	≥15	x 10 ⁹ /L	≤2.8	≥15	
Neutrophils	x 10 ³ /uL	≤1.5	No upper limit	x 10 ⁹ /L	≤1.5	No upper limit	
Platelet Count	x 10 ³ /uL	≤75	≥700	10 ⁹ /L	≤75	≥700	
		Chemistry	(serum or plasma	1)			
ALT (SGPT)	U/L	No lower limit	≥3 X ULN	U/L	No lower limit	≥3 X ULN	
AST (SGOT)	U/L	No lower limit	≥3 X ULN	U/L	No lower limit	≥3 X ULN	
Total Bilirubin	mg/dL	No lower limit	≥1.5 ULN	umol/L	No lower limit	≥1.5 ULN	
BUN	mg/dL	No lower limit	≥30.0	mmol/L	No lower limit	≥10.71	
Creatine Kinase (CK)	U/L	No lower limit	≥3 ULN	U/L	No lower limit	≥3 ULN	
Sodium	mEq/L	≤125	≥155	mmol/L	≤125	≥155	
Potassium	mEq/L	≤3.0	≥5.5	mmol/L	≤3.0	≥5.5	
Calcium, total	mg/dL	<8.0	>11.0	mmol/L	<2.0	>2.75	

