14.3.6.2 Vital Signs Methods of Analysis

Vital signs will be summarized using descriptive statistics at Baseline and all scheduled post-Baseline visits. The change from Baseline values will also be summarized at the scheduled post-Baseline visits.

Vital sign values will be considered PCI if they meet the criteria listed in Table 4. The number and percentage of subjects with post-Baseline vital signs that are PCI will be summarized at scheduled post-Baseline visits and for overall post-Baseline. For the overall post-Baseline summaries, all post-Baseline values will be considered, including unscheduled and out of window values. Subjects with multiple PCI values for a given parameter will be counted only once for that parameter. For the by-visit summary, the numerator for the

percentage is the number of subjects with a post-Baseline PCI value for the given parameter, visit and treatment group, and the denominator is the number of subjects with non-missing values for the given parameter, visit and treatment group. For the overall post-Baseline summary, the numerator for the percentage is the number of subjects with at least 1 post-Baseline PCI value for the given parameter and treatment group, and the denominator is the number of subjects with at least 1 post-Baseline value for the given parameter and treatment group.

A listing of all PCI values will be provided (excluding those vitals collected by persons other than study site staff). There will be a separate PCI listing for vitals collected by persons other than study site staff. These listings will include all observations for those subjects and parameters for which at least one PCI value (including Baseline) was observed.

Table 5 Criteria for Potentiall	y Clinically Important `	Vital Signs
---------------------------------	--------------------------	-------------

		Criteria ^a			
Vital Sign Parameter	Unit	Observed Value	And/Or	Change Relative to Baseline	
Systolic blood pressure	mmHg	≥180	And	Increase of ≥20	
(supine or sitting)		≤90	And	Decrease of ≥20	
Diastolic blood pressure	mmHg	≥105	And	Increase of ≥15	
(supine or sitting)		≤50	And	Decrease of ≥15	
Dulgo (queino on gittino)	bpm	≥120	And	Increase of ≥15	
Pulse (supine or sitting)		≤50	And	Decrease of ≥15	
Weight	1	Not Applicable		Increase of ≥7%	
weight	kg			Decrease of ≥7%	

A post-baseline value is considered as a PCI value if it meets both criteria for observed value and change from baseline.

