14.3.7.2 ECG Methods of Analysis

14.3.7.2.1 Observed Values and Change from Baseline

Observed values and the changes from Baseline of ECG variables will be summarized using descriptive statistics at Baseline and all scheduled post-Baseline visits. For the QTcF categorical analysis, the number and percentage of subject in each category will be summarized at each scheduled visit as well as overall post-Baseline maximum.

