14.3.7.2.3 Cardiologist Interpretations

For cardiologist's interpretations, the number and percentage of subjects with ECG results that are determined as normal or abnormal will be summarized at scheduled visits. The overall post-baseline worst interpretation will also be summarized (i.e. if a subject has one or more ECG results that are considered as abnormal, this subject will be counted in the abnormal category). Cardiologist's interpretations will also be summarized in a shift table to determine the number and percentage of subjects with ECG results classified as normal or abnormal at scheduled post-Baseline visits relative to the same classification at the Baseline visit. The shifts from Baseline to overall post-Baseline worst interpretation will also be presented. For the by-visit shift summary, the denominator is the number of subjects with non-missing cardiologist's interpretation at Baseline and the given visit for the given treatment group. For the summaries of shift from Baseline to the overall post-Baseline worst interpretation, the denominator is the number of subjects with non-missing Baseline and at least 1 post-Baseline cardiologist's interpretation for the given treatment group.

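### The ECG PCI rows for QRS and PR mix abnormalities present at Baseline with new ones, and no planned table counts the new ones by arm

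*SAP*

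**What the plan says.** SAP 14.3.7.2.2 states: "Electrocardiogram values will be considered PCI if they meet or exceed the criteria listed in Table 6". Table 6 has four entries: QRS at or above 120 msec, PR at or above 220 msec, QTcB or QTcF above 500 msec, and a QTcB or QTcF change from Baseline above 60 msec. Only the last refers to Baseline. Across all visits after Baseline taken together, the SAP defines the count as follows: "the numerator for the percentage is the number of subjects with at least 1 post-Baseline PCI value for the given parameter and treatment group". Everyone with any value after Baseline goes into the denominator. The by-visit summary is built the same way, from everyone with a value at that visit.

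Protocol 4.3 allows a wide QRS at entry. Exclusion 11 uses QRS only to choose the QTcF limit, as in "QTcF >470 ms, if QRS duration ≥120 ms". No inclusion or exclusion criterion mentions PR.

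Other PCI tables in the same SAP do take account of Baseline. Laboratory PCI counts "will be summarized by Baseline status (all or within normal range) for selected parameters" (SAP 14.3.5.3), and SAP 14.3.5.2 adds shift tables by parameter: "Laboratory values will be summarized in shift tables to determine the number and percentage of subjects with values classified as below (low), within (normal". For blood pressure and pulse, the footnote to Table 5 says: "A post-baseline value is considered as a PCI value if it meets both criteria for observed value and change from baseline".

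For QRS and PR, the Baseline information elsewhere in the plan is:
- descriptive statistics: "Observed values and the changes from Baseline of ECG variables will be summarized using descriptive statistics at Baseline and all scheduled post-Baseline visits" (SAP 14.3.7.2.1);
- the cardiologist's overall reading, which "will also be summarized in a shift table to determine the number and percentage of subjects with ECG results classified as normal or abnormal" (SAP 14.3.7.2.3);
- listings that include Baseline values (SAP 14.3.7.2.2 and 14.3.7.2.4).

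**The concern.** A subject who enters with QRS of 125 msec and stays there is tabulated as a post-Baseline PCI case, exactly like a subject who moves from 95 to 125 msec. A safety reader wants to know how many subjects in each arm developed the abnormality on treatment, and the table cannot say. If wide QRS or long PR is at all common at entry in subjects aged 60 or over, most of the count could predate the first dose. Chance differences in Baseline prevalence between arms also enter the comparison directly. What is at stake is how clearly one descriptive safety table can be read. The primary measure, the secondary endpoints and every planned test are unaffected.

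**Working it through.** **Plan's own figure.** The documents give no figure for ECG PCI rates. The only sample-size figures are the probabilities of seeing at least one event in 375 subjects, and they reproduce: 1 − 0.99^375 = 0.9769, 1 − 0.985^375 = 0.9965 and 1 − 0.98^375 = 0.99949, against 0.977, 0.997 and 0.999. They do not bear on this point beyond confirming n = 375 per arm.

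**Inputs.** From the documents: n = 375 per arm (SAP 3.5), the Table 6 thresholds, and numerators and denominators without a Baseline condition. Assumed, because the documents are silent: Baseline prevalence b, proportion p of Baseline cases that meet the threshold again after Baseline, and new-onset rate q among subjects free of the abnormality at Baseline. I also assume that every subject has a Baseline and a post-Baseline ECG.

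**Formulas, per arm.** Pre-existing cases = n·b·p. New cases = n·(1 − b)·q. Displayed rate = b·p + (1 − b)·q. Displayed difference = (1 − b)·(q1 − q0), which does not depend on p. With independent arms, the SD of the chance difference in pre-existing cases is √(2·n·bp·(1 − bp)).

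**Results with p = 0.95, q0 = 2% (placebo), q1 = 4% (pimavanserin).**

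| b | Pre-existing cases per arm | New cases, placebo / pimavanserin | Displayed rates | Difference (points) | Pre-existing share of count, placebo / pimavanserin |
|---|---|---|---|---|---|
| 5% | 17.8 | 7.1 / 14.2 | 6.65% v 8.55% | 1.9 | 71% / 56% |
| 10% | 35.6 | 6.8 / 13.5 | 11.3% v 13.1% | 1.8 | 84% / 73% |
| 15% | 53.4 | 6.4 / 12.8 | 15.95% v 17.65% | 1.7 | 89% / 81% |

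Worked line for b = 10%: 375 × 0.10 × 0.95 = 35.6 pre-existing; 375 × 0.90 × 0.02 = 6.75 new on placebo; 0.095 + 0.018 = 11.3%; 0.095 / 0.113 = 84%.

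**Sensitivity.** At b = 2% the placebo share is 0.019 / 0.0386 = 49% and the difference 1.96 points. With p = 0.80 the placebo shares at 5%, 10% and 15% are 0.040 / 0.059 = 68%, 0.080 / 0.098 = 82% and 0.120 / 0.137 = 88%. With onset 1% v 3% and full persistence they are 84%, 92% and 95%, and the difference is again 1.9, 1.8 and 1.7 points.

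**Chance imbalance.** At b = 10% the SD is √(2 × 375 × 0.095 × 0.905) = 8.0 subjects, against an expected excess of new cases of 13.5 − 6.75 = 6.75. A one-SD imbalance in Baseline cases is therefore about as large as the assumed signal.

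**The rows for QTc above 500 msec.**
- *QTcB.* Eligibility limits QTcF, not QTcB. Since QTcB = QTcF × RR^(−1/6), QTcB exceeds 500 when RR < (QTcF/500)^6. At QTcF 470 that is 0.690 s, a heart rate above 87 bpm. At 450 it is 0.531 s, above 113 bpm. Exclusion 12 sets only a lower heart-rate limit; the SAP Introduction mentions a tachycardia exclusion for the Czech Republic only. Baseline cases are possible but probably few.
- *QTcF.* Protocol 6.3.4 lets a subject be enrolled on the local machine reading and discontinued once the central reading proves out of range. The Safety Analysis Set (SAP 4.2) keeps any randomised subject who took one dose, and the early-termination visit includes an ECG (Protocol Table S-1). A Baseline value above 500 can therefore reach the table, though it should be rare.

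**The case against.** The strongest reply is that nothing of consequence changes. This is a descriptive count among other safety analyses. Arms are balanced on average, so the comparison is not biased, and on the absolute scale the assumed 2.0-point difference shows as 1.7 to 1.9. All of that stands.

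A reader might go further and infer that the table hides a true doubling of risk, because the ratio of displayed rates in the example falls from 2.0 to 1.29, 1.16 or 1.11. The documents do not support resting the point on that: the SAP plans counts and percentages, not ratios, and every rate behind those figures is assumed.

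A reader might also infer that the SAP breaks its own rule. It does not. The laboratory split applies to selected parameters and uses the normal range, not the PCI threshold. It is a useful precedent, not a requirement for ECG.

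It is fair to add that the ECG risk named in the protocol background is QT prolongation, and that the plan gives QTcF its own categories. The Baseline data are collected and listed, so new cases could be tabulated later. Table specifications are in a separate document (SAP 1) and may already include such a split.

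These points limit the importance without filling the gap. Change-from-Baseline statistics give no threshold counts. The overall normal/abnormal shift cannot show a new QRS or PR finding in someone already abnormal for another reason. A listing is not a rate by arm. The SAP text does not require the split.

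**Conclusion.** The point holds as a cheap improvement to one safety table. The planned QRS and PR rows combine persisting Baseline abnormalities with new ones, and no table described in the SAP separates them by arm. There is no directional bias, and no primary, secondary or inferential result is touched. What suffers is the new-onset count, together with added noise from chance Baseline imbalance.

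The textual part is firm. The size is not: under 5% to 15% Baseline prevalence, 95% persistence and 2% v 4% onset, pre-existing cases would be 71% to 89% of the placebo count, and the share falls to about half at 2% prevalence.

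One might suppose that QTcF above 500 msec cannot be carried over from Baseline because entry is capped at 470 msec. That is true of subjects whose central reading was in range, but not of everyone in the Safety Analysis Set.

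**What to change.** In SAP 14.3.7.2.2, keep the all-subject rows. For each absolute criterion in Table 6 (QRS, PR and, at the same cost, QTcB above 500 and QTcF above 500 msec), add a row restricted to subjects with a non-missing Baseline value that does not meet that criterion. Use that number as the denominator, applying the existing requirement for a post-Baseline value, overall or at the visit. This resembles the laboratory PCI display by Baseline status. The rows for a change above 60 msec need nothing, since they already refer to Baseline. No threshold changes.

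The cost is a slightly longer table and a few lines of programming on data already collected. One limit should be noted beside the table: the protocol schedules a single ECG at Baseline, so the new rows will still count some crossings that are only measurement variation, such as QRS moving from 119 to 121 msec. They will come closer to new onset without measuring it exactly.

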14.3.7.2.3 Cardiologist Interpretations

For cardiologist's interpretations, the number and percentage of subjects with ECG results that are determined as normal or abnormal will be summarized at scheduled visits. The overall post-baseline worst interpretation will also be summarized (i.e. if a subject has one or more ECG results that are considered as abnormal, this subject will be counted in the abnormal category). Cardiologist's interpretations will also be summarized in a shift table to determine the number and percentage of subjects with ECG results classified as normal or abnormal at scheduled post-Baseline visits relative to the same classification at the Baseline visit. The shifts from Baseline to overall post-Baseline worst interpretation will also be presented. For the by-visit shift summary, the denominator is the number of subjects with non-missing cardiologist's interpretation at Baseline and the given visit for the given treatment group. For the summaries of shift from Baseline to the overall post-Baseline worst interpretation, the denominator is the number of subjects with non-missing Baseline and at least 1 post-Baseline cardiologist's interpretation for the given treatment group.

14.3.7.2.4 Data Listings

All data, including machine-read Baseline results, will be listed. A listing of all PCI values will be provided. This listing will include all observations for those subjects and parameters for which at least one PCI value (including Baseline) was observed.

14.3.8 Physical Examination

Physical examination is performed at Screening, Baseline, Week 4, and Week 8/ET visits.

Physical examination results (normal, abnormal, and not done) at Baseline, Week 4, and Week 8/ET will be summarized in a frequency table by body system and visit.

14.3.9 Suicidality

14.3.9.1 C-SSRS

The C-SSRS will be administered if the subject, in the Investigator's judgement, is able to reliably complete it. Otherwise, the GCAS will be administered and used thereafter in the study.

The event counts and the number and percentage of subjects reporting any post-Baseline suicidal ideation (wish to be dead; non-specific active suicidal thoughts; active suicidal ideation with any methods (not plan) without intent to act; active suicidal ideation with some intent to act, without specific plan; active suicidal ideation with specific plan and intent), suicidal behavior (preparatory acts or behavior; aborted attempt; interrupted attempt; actual attempt; suicide), or suicidality (any suicidal ideation or behavior) will be tabulated.

The event counts and the number and percentage of subjects reporting any post-Baseline non-suicidal self-injurious behavior will also be tabulated.

For calculating the percentages, the denominator will be the number of subjects with at least one post-Baseline C-SSRS assessment within each treatment group.

